The cumulative incidence curve for MR and estimates at 3, 6, 12, 18, 24 and 36 months with 95% confidence intervals will be presented for subjects with underlying hematologic malignant disease, accounting for NRM as the competing risk. In addition, the proportion of subjects who had hematologic malignancy relapse/recurrence and its 95% confidence interval at 3, 6, 12, 18, 24 and 36 months will be presented for subjects with underlying hematologic malignant disease.

Reduction of daily corticosteroid dose

This will be assessed by the proportion of subjects with $\geq 50\%$ reduction from baseline in daily corticosteroid dose at Cycle 7 Day 1, based on all subjects enrolled in the study.

A sensitivity analysis of the same endpoint, to exclude dose interruption of corticosteroids due to AE, might be planned in the Statistical Analysis Plan (SAP) per the alignment across the REACH studies.

Reduction to low dose corticosteroids

This will be assessed by the proportion of subjects with reduction from baseline in daily corticosteroid dose to methylprednisolone-equivalent steroid dose of $\leq 0.2\text{mg/kg/day}$ (or equivalent dose of $\leq 0.25\text{mg/kg/day}$ prednisone or prednisolone) at Cycle 7 Day 1, based on all subjects enrolled in the study.

A sensitivity analysis of the same endpoint, to exclude dose interruption of corticosteroids due to AE, might be planned in the SAP per the alignment across the REACH studies.

Graft Failure

This will be assessed by donor cell chimerism, defined as initial whole blood or marrow donor chimerism for those who had $\geq 5\%$ donor cell chimerism at baseline. If donor cell chimerism declines to $< 5\%$ on subsequent measurements, graft failure is declared. The percentage of graft failure with 95% confidence intervals at 3, 6, 12, 18, 24 and 36 months will be presented. Case descriptions will be used in case of very few subjects with graft failure (e.g. less than 5 subjects).

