• To assess best overall response (BOR)	• Proportion of subjects who achieved OR (CR+PR) at any time point (until Cycle 7 Day 1 or the start of additional systemic therapy for cGvHD)		No repeat of BOR at C7D1, but for BOR up to study end
• To estimate the failure free survival (FFS)	• Composite time to event endpoint incorporating the following FFS events: i) relapse or recurrence of underlying disease or death due to underlying disease, ii) non-relapse mortality, or iii) addition or initiation of another systemic therapy for cGvHD.		Yes
• To assess cumulative incidence of malignancy relapse/recurrence (MR)	• Malignancy relapse/recurrence (MR) is defined as the time from date of treatment assignment to hematologic malignancy relapse/recurrence. Calculated for subjects with underlying hematologic malignant disease.		Yes
• To assess non-relapse mortality (NRM)	• Non-relapse mortality (NRM), defined as the time from date of treatment assignment to date of death not preceded by underlying disease relapse/recurrence.		Yes

Objective(s)	Endpoint(s)	Analysis	Analysis incl. in final CSR

 To assess overall survival (OS) 	
 Overall survival, defined as the time from the date of treatment assignment to the date of death due to any cause. 		Yes

 To assess a reduction of at least $\geq 50\%$ in daily corticosteroid use at Cycle 7 Day 1 	
 Proportion of subjects with $\geq 50\%$ reduction from baseline in daily corticosteroid dose at Cycle 7 Day 1 		No repeat of the data up to C7D1, but analysis will be done considering data up to study end

 To assess a reduction to a low dose corticosteroid dose at Cycle 7 Day 1 	
 Proportion of subjects with reduction from baseline in daily corticosteroid dose to ≤ 0.2 mg/kg/day methylprednisolone (or equivalent dose of ≤ 0.25 mg/kg/day prednisone or prednisolone) at Cycle 7 Day 1 		No repeat of the data up to C7D1, but analysis will be done considering data up to study end

 To assess graft failure 	
 Assess using donor cell chimerism, defined as initial whole blood or marrow donor chimerism for those who had $\geq 5\%$ donor cell chimerism at baseline. If donor cell chimerism declines to $< 5\%$ on subsequent measurements, the graft failure is declared. 		Yes

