An additional analysis of duration of response for responders up to data cut-off date will be done on all subjects with BOR considering all response assessments up to End of Treatment of the subjects or data cut-off date. Note, for subjects who tapered off, all response assessments up to End of Treatment even those collected after ruxolitinib discontinuation will be considered for the analysis.

Overall survival (OS)

Overall survival is defined as the time from date of treatment assignment to date of death due to any cause. If a patient is not known to have died, then OS will be censored at the latest date the patient was known to be alive (last contact date on or before the cut-off date).

Non-Relapse Mortality (NRM)

Non-relapse mortality (NRM), defined as the time from date of treatment assignment to date of death not preceded by underlying malignant or non-malignant disease relapse/recurrence. Underlying disease relapse/recurrence is considered as competing events. If a patient is not known to have died or experienced the competing event, then NRM will be censored at the latest date the patient was known to be event-free (last contact date on or before the cut-off date).

Incidence of Malignancy Relapse/Recurrence (MR)

Incidence of Malignancy Relapse/Recurrence (MR), defined as the time from date of treatment assignment to date of relapse/recurrence of the underlying hematologic malignancy disease. NRM is considered as competing event. If a patient is not known to have a hematologic malignancy relapse/recurrence or died without relapse/recurrence, then incidence of MR will

be censored at the latest date the patient was known to be event-free (last contact date on or before the cut-off date).

Reduction of daily corticosteroid dose

Reduction of daily corticosteroid dose, is defined as the proportion of patients with $\geq 50\%$ reduction from baseline in daily corticosteroid dose due to disease improvement at Cycle 7 Day 1.

For the final CSR the analyses will be done considering data up to end of study.

Reduction to low dose corticosteroids

Reduction to low dose corticosteroids, is defined as the proportion of subjects with reduction from baseline in daily corticosteroid dose to methylprednisolone-equivalent steroid dose of $\leq 0.2\text{mg/kg/day}$ (or equivalent dose of $\leq 0.25\text{mg/kg/day}$ prednisone or prednisolone) due to disease improvement at Cycle 7 Day 1.

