The proportion of subjects with $\geq 50\%$ reduction from baseline in daily corticosteroid dose due to disease improvement at Cycle 7 Day 1, and its 95% confidence interval will be presented based on all subjects in the FAS. For the final CSR the analyses will be done considering data up to end of study.

Reduction to low dose corticosteroids

The proportion of subjects with reduction from baseline in daily corticosteroid dose to methylprednisolone-equivalent steroid dose of $\leq 0.2\text{mg/kg/day}$ (or equivalent dose of $\leq 0.25\text{mg/kg/day}$ prednisone or prednisolone) due to disease improvement at Cycle 7 Day 1, and its 95% confidence interval will be presented based on all subjects in the FAS. For the final CSR the analyses will be done considering data up to end of study.

Graft Failure

The percentage of graft failure with 95% confidence intervals at 3, 6, 12, 18, 24 and 36 months will be presented based on all subjects in the FAS. In case of very few patients with graft failure (e.g. less than 5 patients), case descriptions using listings will be provided instead.

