2.13 Other Exploratory analyses

Chronic GvHD recurrence following completion of a taper of ruxolitinib

This analysis is performed only for patients who taper off ruxolitinib due to achieving a CR or PR. These subjects will be identified as they have reason “responder” for ruxolitinib permanent discontinuation on the exposure CRF. It’s planned to do this analysis at time of final CSR and only if sufficient number of subjects with cGvHD recurrence after tapering off occurred.

Time to recurrence is defined as the time from completion of a taper of systemic therapy until cGvHD recurrence. Patients without event will be censored at the last contact date. Kaplan-

Meier method and the Kaplan-Meier curves as well as survival probabilities at appropriate time points will be presented with 95% confidence intervals ([Brookmeyer and Crowley 1982](#)).

In case of single subjects (less than 5 subjects) with cGvHD recurrence after tapering off, data will be reported in listing only.

Systemic corticosteroid-free response rate

Systemic corticosteroid-free response rate is defined as the proportion of subjects taking no systemic corticosteroid therapy since at least 1 month (i.e. time between date of last corticosteroid drug intake and response assessment data is ≥ 30 days) and demonstrating a complete response (CR) or partial response (PR), at any time post-baseline. Subjects who didn't receive corticosteroids at baseline and still not taking corticosteroids at time of response will be considered as corticosteroid-free responder. Initiation of any new systemic therapy after cGvHD flare or recurrence, regardless when, means treatment failure and the subject is considered as non-responder. The endpoint is similar to the primary endpoint ORR, but considers all subjects who could not taper off systemic corticosteroids as non-responder regardless if they are in CR or PR, and considers all response assessments up to End of Treatment of the subject or data cut-off date.

Systemic corticosteroid-free response rate and its 90% confidence interval will be presented based on all subjects in the FAS and by subgroup of treatment naive cGvHD vs SR-cGvHD.

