49	31	0.63	0.881	0.505	0.747
50	32	0.64	0.859	0.514	0.753

4 Change to protocol specified analyses

One exploratory analysis endpoints is added:

Chronic GvHD recurrence following completion of a taper of systemic therapy (see [Section 2.13](#)).

5 Appendix

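### SAP 2.7.1 and 2.7.2 count a steroid reduction only if it is due to disease improvement; the protocol's any-cause endpoints have no specified analysis, and the change is undeclared

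*SAP*

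**What the plan says.** The protocol has two steroid-sparing secondary endpoints at Cycle 7 Day 1. One is a fall of at least 50% in daily dose. The other is a fall to at most 0.2 mg/kg/day methylprednisolone or equivalent. Neither asks why the dose fell. For the first, Protocol 12.5.1 reads "reduction from baseline in daily corticosteroid dose at Cycle 7 Day 1, based on all subjects enrolled in the study", and the low-dose endpoint uses the same population. The only variant based on cause is optional: "A sensitivity analysis of the same endpoint, to exclude dose interruption of corticosteroids due to AE, might be planned".

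SAP 2.7.1 defines the first endpoint as a "reduction from baseline in daily corticosteroid dose due to disease improvement at Cycle 7 Day 1" and adds the same condition to the second. SAP 2.7.2 analyses that version of each: "due to disease improvement at Cycle 7 Day 1, and its 95% confidence interval will be presented based on all subjects in the FAS". SAP Table 1-1 keeps the protocol definition, "reduction from baseline in daily corticosteroid dose at Cycle 7 Day 1", with no condition.

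SAP Section 4, where departures from the protocol's analyses are declared, has one entry: "One exploratory analysis endpoints is added". That entry concerns recurrence after tapering. The document history mentions the steroid endpoints only for their extension to end-of-study data. It also has a general line about clarification and alignment with other studies in the project, which does not name this change.

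**The concern.** The condition changes what is estimated. The protocol endpoint asks how many children had their steroid dose cut to the required extent. The SAP version asks how many had it cut for one particular reason. It also goes further than the protocol's optional sensitivity analysis, which would set aside only interruptions due to adverse events. The SAP sets aside every reduction not attributed to improvement.

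Reductions for other reasons are foreseeable. Protocol 6.5.1 lets the steroid dose be modified at the investigator's discretion, by institutional guideline or by label. The early-taper deviation code in SAP 2.5.4 (TRT13) sets aside dose adjustments made for safety. So the two definitions can give different numbers.

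Steroid sparing is a named expected benefit in Protocol 1.2. A reader who takes the definition from Table 1-1 would read the reported rate as the any-cause rate. With no derivation stated, two programmers could also classify the same subject differently.

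**Working it through.** The plan gives no figure for the steroid endpoints. Its one design figure concerns the primary endpoint: with 42 subjects, at least 27 responders and a true response rate of 70%, the probability that the lower 90% limit is at least 50% is stated as 0.836. The exact binomial tail gives 0.8360, and the 90% limits at 27/42 are 0.505 and 0.765, as tabulated. This point does not touch those figures.

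**The definitions side by side**

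| Place | Condition on cause | Population |
|---|---|---|
| Protocol Table 2-1 | none | not stated |
| Protocol 12.5.1 | none (optional sensitivity analysis for AE interruptions) | all enrolled |
| SAP Table 1-1 | none | not stated |
| SAP 2.7.1 | disease improvement | not stated |
| SAP 2.7.2 | disease improvement | all FAS subjects |

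The SAP sections that direct the analysis agree with each other. They disagree with the protocol and with the SAP's own objectives table.

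**Size**

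Inputs: 46 subjects enrolled (Protocol, Amendment 2 summary). Taking the FAS as 46 is an assumption, because SAP 2.2 removes subjects without written consent or treated beyond local regulatory requirements and states no FAS count. Let X be the subjects with a qualifying reduction for any reason, and a those whose reduction had another cause. Neither is in the documents.

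- Protocol endpoint = X/46
- SAP endpoint = (X − a)/46
- Difference = a/46, and one subject is 1/46 = 2.2 points

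| X (assumed) | a = 0 (protocol rate) | a = 2 | a = 4 | a = 6 |
|---|---|---|---|---|
| 20 | 43.5% | 39.1% | 34.8% | 30.4% |
| 25 | 54.3% | 50.0% | 45.7% | 41.3% |
| 30 | 65.2% | 60.9% | 56.5% | 52.2% |

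The gap is 4.3, 8.7 and 13.0 points for a = 2, 4 and 6, whatever X is. For scale, the exact 95% interval for 25/46 runs from 39.0% to 69.1%.

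**Baseline dose, a separate and smaller matter**

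Neither document has a rule for these two endpoints when the baseline dose is zero or already at or below 0.2 mg/kg/day. A subject with no baseline dose cannot show a reduction but stays in the denominator. A subject already at or below the threshold meets the low-dose wording of the protocol with any decrease. SAP 2.13 foresees the zero case, but only for the exploratory steroid-free response: there, subjects who did not "receive corticosteroids at baseline and still not taking corticosteroids at time of response" count as corticosteroid-free responders. If m of 46 had no baseline dose and X = 25, the any-cause rate among the rest would be 25/43 = 58.1% for m = 3 or 25/40 = 62.5% for m = 6, against 54.3%. These values of m are illustrations only.

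**The case against.** The condition is conservative: it can only remove successes, so it cannot flatter the drug. Protocol 6.1.5 and 6.1.5.2 tie steroid tapering to a documented response, so most protocol-compliant tapers would satisfy it and the two rates may be close. The protocol itself foresaw a cause-based refinement in the SAP, aligned with the sister studies. These are descriptive secondary endpoints in a single-arm study with no hypothesis tests. All of that stands and keeps the point minor. It does not explain why the conditional version became the only specified analysis, or why that is not declared.

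Four stronger readings are tempting, and the documents do not support them:

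- **That the protocol endpoint is never reported.** Table 1-1 still lists it and says the Cycle 7 Day 1 analysis is not repeated for the final report. The interim report is not available here. What can be said is that no analysis of the unconditional endpoint is specified.
- **That the SAP introduced the all-subjects denominator.** Protocol 12.5.1 already uses all enrolled subjects, so any dilution by zero-baseline subjects applies to both versions.
- **That many subjects lacked a baseline dose.** Protocol 6.1 requires steroids in both strata, and initial omission in treatment-naive subjects is a deviation (TRT03, SAP 2.5.4). Such subjects should be few, and no count is given.
- **That the result rests on an open-label investigator's reason field.** SAP 2.4.1 describes such a field for ruxolitinib. For steroids it is a plausible inference, not a stated derivation.

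**Conclusion.** The point holds as a discrepancy to correct. SAP 2.7.1 and 2.7.2 make both steroid-reduction endpoints conditional on disease improvement and specify no analysis of the endpoints the protocol defines. This conflicts with SAP Table 1-1, is missing from Section 4 and has no stated derivation for steroids.

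The effect runs downward only: about 2.2 points per subject whose reduction had another cause, if the FAS is 46. The total cannot be known from the documents and would be zero if every reduction followed improvement. The primary endpoint and sample size are unaffected. The missing rule for zero or already-low baseline doses is secondary and is shared by protocol and SAP.

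**What to change.** 1. Report the protocol-defined any-cause endpoint as the main analysis for both steroid measures, with the disease-improvement version as a sensitivity analysis. Because Table 1-1 marks the Cycle 7 Day 1 results as not repeated, include the any-cause rows in the final report if the interim report lacks them.
2. State the data field and rule by which the cause of a steroid reduction is derived.
3. Make 2.7.1 and 2.7.2 agree with Table 1-1, and list the conditional version in Section 4.
4. Optionally, add a supportive row restricted to subjects with baseline dose above zero (50% endpoint) and above 0.2 mg/kg/day methylprednisolone-equivalent (low-dose endpoint), with the number excluded. This is not a protocol analysis and should be labelled so.

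The cost is a few table rows and short text edits. Steroid doses are already collected.

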2.7.2 Statistical hypothesis, model, and method of analysis

Failure Free Survival

The FFS distribution will be estimated using the Kaplan-Meier method, and the Kaplan-Meier curves, medians, 3, 6, 12, 18, 24 and 36 months FFS estimates and 95% confidence intervals ([Brookmeyer and Crowley J. 1982](#)) will be presented based on all subjects in the FAS.

The cumulative incidence curve of each of the three FFS components (considering the other two components as a competing risk) as well as estimates at 3, 6, 12, 18, 24 and 36 months will also be presented with 95% confidence intervals.

Best overall response (BOR)

BOR up to Cycle 7 Day 1 as well as BOR up to data cut-off date and its 90% confidence interval will be presented based on all subjects in the FAS.

ORR at Cycle 4 Day 1 (end of Cycle 3)

ORR (CR+PR) at Cycle 4 Day 1 and its 90% confidence interval will be presented based on all subjects in the FAS.

Duration of Response

Duration of response will be calculated for all patients with BOR = CR or PR up to Cycle 7 Day 1 as well as for all patients with BOR up to data cut-off date = CR or PR. Kaplan-Meier method and the Kaplan-Meier curves, medians, 3, 6, 12, 18, 24 and 36 months survival

probabilities with 95% confidence intervals will be presented based on these responder subjects in the FAS.

Overall survival (OS)

The OS distribution will be estimated using the Kaplan-Meier method, and the Kaplan-Meier curves, medians, 3, 6, 12, 24 and 36 month survival probabilities and 95% confidence intervals ([Brookmeyer and Crowley J. 1982](#)) will be presented based on all subjects in the FAS.

Non-Relapse Mortality (NRM)

Cumulative incidence of NRM and derived probabilities at Months 1, 2, 6, 12, 18, 24 and 36 with 95% confidence intervals will be estimated based on all subjects in the FAS, considering underlying disease relapse/recurrence as competing events ([Gooley et al. 1999](#)).

Incidence of Malignancy Relapse/Recurrence (MR)

The cumulative incidence curve for MR and estimates at 3, 6, 12, 18, 24 and 36 months with 95% confidence intervals will be presented for subjects with underlying hematologic malignant disease, accounting for NRM as the competing risk. In addition, the proportion of subjects who had hematologic malignancy relapse/recurrence and its 95% confidence interval at 3, 6, 12, 18, 24 and 36 months will be presented for subjects with underlying hematologic malignant disease.

Reduction of daily corticosteroid dose

The proportion of subjects with $\geq 50\%$ reduction from baseline in daily corticosteroid dose due to disease improvement at Cycle 7 Day 1, and its 95% confidence interval will be presented based on all subjects in the FAS. For the final CSR the analyses will be done considering data up to end of study.

Reduction to low dose corticosteroids

The proportion of subjects with reduction from baseline in daily corticosteroid dose to methylprednisolone-equivalent steroid dose of $\leq 0.2\text{mg/kg/day}$ (or equivalent dose of $\leq 0.25\text{mg/kg/day}$ prednisone or prednisolone) due to disease improvement at Cycle 7 Day 1, and its 95% confidence interval will be presented based on all subjects in the FAS. For the final CSR the analyses will be done considering data up to end of study.

Graft Failure

The percentage of graft failure with 95% confidence intervals at 3, 6, 12, 18, 24 and 36 months will be presented based on all subjects in the FAS. In case of very few patients with graft failure (e.g. less than 5 patients), case descriptions using listings will be provided instead.

2.7.3 Handling of missing values/censoring/discontinuations

Patients with missing assessments that prevent the evaluation of the ORR at Cycle 4 Day 1 and BOR will be considered non-responders. This includes missing overall cGvHD response assessments at baseline and/or Cycle 4 Day 1. The time window for the Cycle 4 Day 1 visit is defined in [Table 2-1](#) above.

2.8 Safety analyses

For all safety analyses, the safety set will be used. All listings and tables will be presented by Age group. For safety evaluations (except for AE), the last available assessment on or before the date of start of study treatment is taken as the “baseline” assessment.

Safety summaries (tables, figures) include only data from the on-treatment period with the exception of baseline data which will also be summarized where appropriate (e.g. change from baseline summaries). In addition, a separate summary for death including on treatment and post treatment deaths will be provided. In particular, summary tables for (AEs) will summarize only on-treatment events, with a start date during the on-treatment period (*treatment-emergent* Aes).

The on-treatment period lasts from the date of first administration of ruxolitinib to 30 days after the date of the last actual administration of ruxolitinib, see definitions in Section 2.1.1.

2.8.1 Adverse events (AEs)

For reporting of AEs, the overall observation period will be divided into mutually exclusive categories, including pre-treatment, on-treatment, post-treatment periods as defined in [Section 2.1.1](#).

AE summaries will include all Aes occurring (new or worsening) during on-treatment period. All Aes collected in the AE eCRF page will be listed along with the information collected on those Aes e.g. AE relationship to study drug, AE outcome etc. Aes with start date outside of on-treatment period will be flagged in the listings.

Aes will be summarized by number and percentage of patients having at least one AE, having at least one AE in each primary system organ class (SOC) and for each preferred term (PT) using MedDRA coding. A patient with multiple occurrences of an AE will be counted only once in the respective AE category. A patient with multiple CTCAE grades for the same preferred term will be summarized under the maximum CTCAE grade recorded for the event. AE with missing CTCAE grade will be included in the ‘All grades’ column of the summary tables.

In AE summaries, the primary system organ class will be presented alphabetically, and the preferred terms will be sorted within primary SOC in descending frequency. The sort order for the preferred term will be based on the descending frequency in the ruxolitinib arm.

The following adverse event summaries will be produced by group; overview of adverse events and deaths, Aes by SOC and PT, summarized by relationship (all Aes and Aes related to study treatment), seriousness (SAEs and non-SAEs), leading to treatment discontinuation, leading to dose interruption/adjustment, and leading to fatal outcome.

In addition, summary table and listing will be provided for COVID-19 related Aes.

